5.1.3 Subject Exclusion Criteria

The subject must be excluded from participating in the trial if the subject:

1. Currently has active or progressive metastatic disease. (Chest X-ray, Computerized Tomography [CT] urogram or Magnetic Resonance Imaging [MRI] and urogram are allowed to ascertain the superficial nature of the disease when indicated, but not required. If urogram protocol is not available or contrast allergy/poor renal function precludes such imaging, then non-contrast CT or MRI of the abdomen/pelvis within 90 days of study entry will suffice.)
2. Is currently participating in or has participated in a study of an investigational agent or using an investigational device within 4 weeks of the first dose of treatment.
3. Has a diagnosis of immunodeficiency or is receiving systemic steroid therapy or any other form of immunosuppressive therapy within 7 days prior to the first dose of trial treatment.
4. Has had a prior monoclonal antibody within 4 weeks before study Day 1 or who has not recovered (i.e., \leq Grade 1 or at baseline) from adverse events due to agents administered more than 4 weeks earlier.
5. Has had prior systemic chemotherapy, targeted small molecule therapy, or radiation therapy for bladder cancer.
6. If subject received major surgery, they must have recovered adequately from the toxicity and/or complications from the intervention prior to starting therapy.
7. Has a known additional malignancy that is progressing or requires active treatment. Exceptions include basal cell carcinoma of the skin, squamous cell carcinoma of the skin, or in situ cervical cancer that has undergone potentially curative therapy. Upper urinary

tract transitional cell carcinoma is also allowable on study as high risk transitional cell carcinoma is commonly multifocal, and intraluminal BCG therapy is also used for treatment of upper urinary tract lesions in a manner similar to that of bladder tumors.

8. Active autoimmune disease that has required systemic treatment in the past 2 years (i.e. with use of disease modifying agents, corticosteroids or immunosuppressive drugs). Replacement therapy (e.g. thyroxine, insulin, or physiologic corticosteroid replacement therapy for adrenal or pituitary insufficiency, etc.) is not considered a form of systemic treatment.
9. Has evidence of interstitial lung disease or active, non-infectious pneumonitis.
10. Has an active infection, including a concurrent febrile illness, requiring systemic therapy.
11. Has a history or current evidence of any condition, therapy, or laboratory abnormality that might confound the results of the trial, interfere with the subject's participation for the full duration of the trial, or is not in the best interest of the subject to participate, in the opinion of the treating investigator.
12. Has known psychiatric or substance abuse disorders that would interfere with cooperation with the requirements of the trial.
13. Is pregnant or breastfeeding, or expecting to conceive or father children within the projected duration of the trial, starting with the screening visit through 4 months after the last dose of trial treatment.
14. Has received prior therapy with an anti-PD-1, anti-PD-L1, anti-PD-L2, anti-CD137, or anti-Cytotoxic T-lymphocyte-associated antigen-4 (CTLA-4) antibody (including ipilimumab or any other antibody or drug specifically targeting T-cell co-stimulation or checkpoint pathways) including anti-CD40 and anti-OX40 antibodies.
15. Has a known history of Human Immunodeficiency Virus (HIV) (HIV 1/2 antibodies).
16. Has known active Hepatitis B (e.g., HBs Ag reactive) or Hepatitis C (e.g., HCV RNA [qualitative] is detected).
17. Has known active tuberculosis. Subjects will not be specifically tested for the study; however, subjects who are tested within 28 days of beginning study or while on study and test positive with the PPD test before treatment should have active tuberculosis ruled out before therapy begins for their superficial bladder cancer.
18. Has received a live vaccine within 30 days prior to the first dose of trial treatment.
19. Has an active urinary tract infection, gross hematuria, or known broken mucosal barrier of the bladder.
20. Less than 14 days post bladder biopsy, TUR, or traumatic catheterization.

Product: MK-3475

Protocol/Amendment No.: Amendment 5, 21 October 2019

21. Evidence of muscle invasive bladder cancer.
22. Current Pneumonitis or has a history of (non-infectious) pneumonitis that required steroids.

NOTE: Patients in frequent contact with immunosuppressed individuals should be carefully assessed for potential benefits and risks of BCG therapy before initiating treatment.

5.2 Trial Treatments

The treatments to be used in this trial are outlined below in **Table 2**.

Table 2: Trial Treatment

Drug	Dose/Potency	Dose Frequency	Route of Administration	Regimen/Treatment Period	Use
MK-3475 ^{a, b}	100 mg	Every 21 days	IV infusion	6 cycles	Experimental
MK-3475 ^b	200 mg	Every 21 days	IV infusion	6 cycles	Experimental
BCG	1 vial	Every 7 days	Bladder Instillation	6 cycles	Approved

^aThe first 3 subjects will be dosed at 100 mg. If the Data Safety Review Team approves, the dose will be escalated to 200 mg with the fourth subject enrolled.

^bThe MK-3475 dosing interval may be increased due to toxicity as described in Section 5.2.3.3. BCG treatment may be interrupted or delayed as per the instructions for use supplied with BCG (Section 5.2.1.1.3).

BCG: One vial of BCG suspended in 50 ml preservative-free saline. BCG is to be given through a urinary catheter (intravesically) into the bladder. BCG treatment will occur once per week for 6 weeks. BCG treatment will commence on the 3rd cycle of treatment with MK-3475, Week 7. BCG is a FDA approved treatment and will be supplied commercially through the study site pharmacy.

5.2.1 BCG Treatment

5.2.1.1 BCG treatment will be according to Institutional standard for the site; however, the BCG will be provided by MERCK due to the BCG shortage to ensure completion of the study.

For patients with multi-focal disease, it is highly recommended that the patient have a urologic stent and catheter placed prior to the first pembrolizumab treatment to allow for stabilization of the mucosa prior to the start of treatment with BCG. Placement will be at the discretion of the treating physician.

5.2.1.1.1 Dose Selection

The rationale for the use of the indicated dose of BCG is based upon FDA approved and commercially provided package insert/instructions for use of the product. Dosing for the intravesical treatment of carcinoma *in situ* and for the prophylaxis of recurrent papillary tumors consists of one vial of BCG suspended in 50 ml preservative-free saline. The

preparation of the BCG suspension will be completed using aseptic technique and according to FDA approved labeling and use information. Patients with multi-focal disease may have treatment with more than one vial to ensure treatment of all tumor sites (generally kidney or ureter in addition to bladder). Essentially to allow for proper treatment, it is anticipated that one vial will be used to treat each organ/distinct urologic structure.

5.2.1.1.2 Preparation

Consult FDA approved package insert for instructions on BCG preparation (Appendix C has the insert for TICE[®] BCG, there are other manufacturers of BCG that may also be utilized.)

5.2.1.1.3 Dose Delay

BCG treatment will be withheld for Grade ≥ 2 hematuria, Grade ≥ 1 fever and drug-related Grade 4 hematologic toxicities, and all other non-hematological toxicity Grade ≥ 3 adverse effects, including laboratory abnormalities, and severe or life-threatening AEs. Treatment should be postponed until resolution of febrile illness, urinary tract infection, or gross hematuria and adverse effect resolution to Grade ≤ 1 . The treating Investigator who is a qualified physician may delay treatment for Grade 1 and 2 adverse effects if the treating Investigator believes it is in the best interest of the patient. In the event of a grade 1 or 2 immune related adverse event requiring corticosteroid treatment, BCG treatment may be delayed for up to 2 weeks with the expectation that steroid treatment will be discontinued prior to the next BCG treatment cycle. A delay of longer than 2 weeks will permanently discontinue the patient from BCG treatment within the study or permanent withdrawal of the patient from the study. The choice will be at the discretion of the treating Investigator. Steroid treatment for grade 3 or higher immune mediated events will require discontinuation of BCG treatment and/or withdrawal from the study.

Instillation of BCG with an actively bleeding mucosa may promote systemic BCG infection. Therefore, treatment will be postponed for at least two weeks following transurethral resection, biopsy, traumatic catheterization, or gross hematuria.

Patients will be asked to report any fever or flu-like symptoms to their treating Investigator immediately, as well as any systemic manifestations increasing in intensity with repeated instillations, or local symptoms (frequency, urgency, burning sensation with urination) lasting more than 2-3 days. If a patient develops persistent fever or experiences an acute febrile illness consistent with BCG infection, BCG treatment will be discontinued and the patient immediately evaluated and treated for systemic infection. Intravesical instillations of BCG will also be postponed during treatment with antibiotics, since antimicrobial therapy may interfere with the effectiveness of BCG.

5.2.1.1.4 Monitoring for Systemic Dissemination of BCG

To ensure early identification of systemic BCG infection, subjects will be monitored for symptoms of systemic infection. For each cycle of BCG treatment, subjects will be telephoned on Days 2-4 (Treatment is Day 1) of Treatment Weeks 7-12 to inquire about any

symptoms they may be experiencing. In addition to this, each patient will be provided with a thermometer and diary and asked to record oral temperatures each morning and evening throughout the BCG treatment (Weeks 7-12) and for recording of any other symptoms they may be experiencing.

5.2.1.2 Timing of Dose Administration

BCG treatment should be administered beginning on Day 1 of Cycle 3 (Week 7) of MK-3475 after all procedures/assessments have been completed as detailed on the Trial Flow Chart (Section 7.0). BCG treatment will be repeated every 7 days at weeks 8, 9, 10, 11, and 12. BCG treatment may be administered up to 1 day before or after the scheduled date (at 7 days) due to administrative reasons.

All trial treatments will be administered on an outpatient basis and according to institutional standards

5.2.1.3 Drug/Treatment

BCG is given through a urinary catheter (intravesically) into the bladder. BCG will be instilled into the bladder according to institutional standards based on FDA approved indications for treatment of bladder cancer. Additional lesions in patients with multi-focal disease will be treated per institutional standards and directed by the treating urologist. The treatment will be given once a week for 6 weeks.

5.2.1.4 Risks/Adverse Effects of BCG Treatment

For specific information, please see package insert in Appendix C.

Common Side Effects ($\geq 20\%$)

- Dysuria (painful urination)
- Urinary frequency
- Flu-like symptoms
- Hematuria (blood in urine)
- Fever

Less Common Side Effects (4-20%)

- Malaise/ fatigue
- Cystitis (inflammation of the bladder)
- Urgency
- Nocturia
- Cramping or pain in bladder
- Chills
- Nausea
- Incontinence

Rare Side Effects (<4%)

- Anemia

BCG sepsis
BCG infection in other organs
Coagulopathy
Contracted Bladder
Epididymitis/prostatitis
Hepatic Granuloma
Hepatitis
Leukopenia
Orchitis
Pneumonitis
Urinary obstruction

Subjects may develop symptoms of bladder irritability related to the inflammatory response induced by BCG, as well as hematuria following BCG intravesicular treatment. The symptoms typically begin 4-6 hours after instillation and last 24-72 hours. The irritative side effects are usually seen following the third instillation, and tend to increase in severity after each administration. The irritative bladder adverse effects can usually be managed symptomatically with products such as pyridium, propantheline bromide, oxybutynin chloride and acetaminophen. Symptom management will be at the discretion of the treating Investigator. If the patient develops hematuria, then treatment must be postponed until urine is clear again. See dose modification/delay (section 5.2.1.5) for further instruction. No dose reduction or antibiotic treatment has been proven to prevent or decrease bladder irritation related to BCG.

Subjects may develop “Flu-like” symptoms (malaise, fever, and chills) which often reflect hypersensitivity reactions, and can be treated symptomatically with antihistamines (Prophylactic treatment with antihistamine before subsequent BCG courses is left to the discretion of the provider.).

The most serious complication of BCG is disseminated BCG sepsis with associated mortality. In addition, infections have been reported in lung, liver, bone, bone marrow, kidney, regional lymph nodes, and prostate in patients who have received intravesical BCG. Some male genitourinary tract infections (orchitis/epididymitis) have been resistant to multiple drug anti-tuberculous therapy and required orchiectomy. These complications were reported in less than 1% of patients.

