5.2.4 Schedule Modification for Combination Therapy

The dosing schedule of the combination therapy will not be altered except on an individual drug basis (such as holding either individual BCG or MK-3475 therapy) if the time period is for 2 weeks or less. That is to say holding either of the two medications included in the combination therapy for less than two weeks should not affect the dosage schedule for the other medication. Patients will be discontinued from the trial if one of the two medications is held for more than 2 weeks because of toxicity. BCG treatment may continue, after a 2 week hold, outside of the study at the discretion of the treating Investigator.

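### The BCG hold rules for haematuria conflict on threshold and restart, and after gross haematuria the minimum wait can equal or exceed the two-week removal limit, depending on an undefined clock

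*Combined protocol and SAP*

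**What the plan says.** Four sections of the protocol bear on holding BCG for haematuria.

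- **5.2.1.4 (Risks/Adverse Effects of BCG Treatment)**: "If the patient develops hematuria, then treatment must be postponed until urine is clear again". No grade is attached. The reader is sent to 5.2.1.5 for delay instructions.
- **5.2.1.5 (Dose Modification for BCG)**: states only that the BCG dose will not be modified. It has no rule on delay.
- **5.2.1.1.3 (Dose Delay)**: "BCG treatment will be withheld for Grade ≥ 2 hematuria". The investigator "may delay treatment for Grade 1 and 2 adverse effects". The restart condition is "Treatment should be postponed until resolution of febrile illness, urinary tract infection, or gross hematuria and adverse effect resolution to Grade" 1 or lower. Its next paragraph, on actively bleeding mucosa, adds that "treatment will be postponed for at least two weeks following transurethral resection, biopsy, traumatic catheterization, or gross hematuria".
- **5.2.4 (Schedule Modification for Combination Therapy)**: "Patients will be discontinued from the trial if one of the two medications is held for more than 2 weeks because of toxicity". Its first sentence leaves the schedule of the other drug alone "if the time period is for 2 weeks or less". The sentence after it, offered as a restatement, covers only holds shorter than two weeks.

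No section says whether a hold is counted from the bleed, from its resolution or from the missed dose.

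**The concern.** A site with a bleeding patient must answer four questions: whether to hold, until when, for how long at least, and when the patient has to leave. The sections answer the first two differently. They also set a minimum and a maximum of the same length without a common starting point.

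Haematuria is on the protocol's list of common BCG effects. Urinalysis, which includes blood (Table 7), precedes every instillation, and section 8.1.6.2.1 makes treatment depend on an acceptable result without defining acceptable. The situation will therefore be looked for every week from week 7 to week 12.

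The stakes are safety, because 5.2.1.1.3 links instillation onto bleeding mucosa to systemic BCG infection, and consistency of BCG exposure and discontinuation across sites. With 15 subjects, one subject handled differently is 1/15 = 6.7 percentage points of any reported proportion.

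**Working it through.** The plan states no figure to reproduce. The check compares the rules and then counts days.

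**1. Threshold and restart, Grade 1 haematuria**

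| | 5.2.1.4 | 5.2.1.1.3 |
|---|---|---|
| Hold | mandatory | optional |
| Restart | when urine is clear | at Grade 1 or lower, so already met |

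The same patient on the same day must be held under one section and may be treated under the other.

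**2. Gross haematuria: minimum wait against removal limit**

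Inputs:
- weekly instillation (5.2.1.2), so with the last dose at t = 0 the next is due at t = 7 days;
- minimum wait of 14 days (5.2.1.1.3);
- removal after more than 14 days (5.2.4);
- typical onset 4 to 6 hours after instillation, i.e. a = 0.17 to 0.25 days, and duration d = 1 to 3 days (5.2.1.4). Applying this course to gross haematuria is an assumption.

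Formulas:
- earliest restart R = a + 14 if the wait runs from onset, or a + d + 14 if it runs from resolution;
- hold H = R − a if counted from onset, or R − 7 if counted from the missed dose;
- days left = 14 − H.

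| Wait from | Hold from | R | H | Days left |
|---|---|---|---|---|
| onset | onset | a + 14 | 14 | 0 (day 14 only) |
| resolution | onset | a + 15 to a + 17 | 15 to 17 | −1 to −3 (none) |
| onset | missed dose | 14.17 to 14.25 | 7.17 to 7.25 | 6.75 to 6.83 |
| resolution | missed dose | 15.17 to 17.25 | 8.17 to 10.25 | 3.75 to 5.83 |

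Two variations:
- **Late bleed.** With the wait from resolution and the hold from the missed dose, H = a + d + 7, which exceeds 14 whenever a + d > 7. A bleed that starts on the dosing day (a = 7) and lasts 1 to 3 days gives H = 15 to 17. If the wait runs from onset, H = 14 exactly.
- **Weekly slots.** If restart must fall exactly on a weekly slot, the first slot in the last two rows is t = 21, so H = 21 − 7 = 14. That is within the limit as worded in the first sentence of 5.2.4 and in its removal sentence, but outside the range in the sentence between them. The one-day visit window in 5.2.1.2, if it applied (it is for administrative reasons), would let the onset-based case use the slot at t = 14, with a hold of about 7 days.

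**3. How often**

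Section 5.2.1.4 lists haematuria, without grade, at 20% or more. The expected number is at least 15 × 0.20 = 3. If subjects are independent, the chance of at least one is at least 1 − 0.8^15 = 0.965. The documents split this neither into Grade 1 and higher nor into gross and microscopic, so the figures describe how often a haematuria rule is consulted, not how often the two-week limits meet.

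**The case against.** The best defence has four parts.

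*The threshold conflict is mild.* Section 5.2.1.1.3 permits delay for Grade 1, so a site that holds for any haematuria breaks neither section. Clear urine may also mean no visible blood, which would limit 5.2.1.4 to gross haematuria. The first part is true, but a site that treats at Grade 1 complies with one section and breaks the other. The second reading removes the Grade 1 conflict, but leaves an open-ended rule (until clear) beside a fixed minimum for the same event and does not touch the two-week limits.

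*The delay rule can be found.* It sits under a Dose Delay heading, and Table 2, footnote b, points to it correctly. That makes the reference to 5.2.1.5 an editorial error, but one that leads a reader of the haematuria sentence to no rule.

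*Nothing is held until a weekly dose is missed.* On that count, a typical early bleed leaves about 4 to 7 days. This stands. A reader might infer that every gross bleed leaves a single restart day or forces removal. The documents do not support that: it needs the hold counted from the bleed, a bleed on the dosing day, or restart on exact weekly slots, and none of these is fixed.

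*The effect on results is not shown.* Treated subjects are not replaced, enrolled subjects stay in the intent-to-treat population (5.7), those who stop treatment for reasons other than progression go on to follow-up (8.1.6.6), and the analysis is descriptive (10.1). This also stands: no bias of stated size follows. What remains is variation in BCG exposure and discontinuation produced by the wording.

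**Conclusion.** The point holds as an internal inconsistency. For Grade 1 haematuria the sections give opposite instructions. For gross haematuria the two-week minimum can equal or exceed the two-week removal limit: the days left range from about 7 to none, according to a clock that the protocol does not define. The 4 to 7 day figure rests on the protocol's typical symptom timing and on counting from the missed dose.

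The expected 3 or more of 15 subjects, and the 96% chance of at least one, apply to haematuria of any grade. A reader might take them as the frequency of the restart clash. They are not, because the minimum wait covers gross haematuria only and no rate for that is given. The correction should be made because it affects stated safety and removal rules. It does not show that the trial's results would be wrong.

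**What to change.** Sections 5.2.1.1.3, 5.2.1.4, 5.2.1.5 and 5.2.4 must be reconciled into one statement that gives:

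1. the haematuria threshold for a mandatory hold;
2. the restart condition;
3. the minimum wait after gross haematuria, and whether it replaces or adds to the resolution rule;
4. the day on which the wait and the hold each start;
5. whether a hold of exactly two weeks is within or beyond the limit.

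The reference in 5.2.1.4 to 5.2.1.5 should point to wherever that statement stands. Which clinical rule applies is for the sponsor to decide. The cost is protocol wording; sample size and analysis do not change.

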5.2.1.5 Dose Modification for BCG

BCG dose modification has not been shown to reduce toxicity; therefore, no dose modifications will be attempted in this trial.

5.2.1.6 Over Dosage

Over dosage occurs if more than one vial (per treated organ/urologic structure) of BCG is administered per instillation. If over dosage occurs, the patient should be closely monitored for signs of active local or systemic BCG infection. For acute local or systemic reactions

Product: MK-3475

Protocol/Amendment No.: Amendment 5, 21 October 2019

suggesting active infection, an infectious disease specialist experienced in BCG complications should be consulted.

5.2.2 MK-3475 Treatment

5.2.3 Dose Selection/Modification

5.2.3.1 Dose Selection

The rationale for selection of doses to be used in this trial is provided in Section 4.0 - Background and Rationale.

A fixed dose of 100 mg MK-3475 will be given on Day 1 +/-3 days of a 21 day cycle for up to 6 cycles for the first 3 subjects. If one subject of the three requires the dose of MK-3475 to be withheld or discontinued, the 100 mg cohort will be expanded to 6 subjects. If two out of three or two out of six subjects develops toxicity that requires the dose to be withheld or discontinued, the dose will not be escalated to 200 mg MK-3475 every 3 weeks. All remaining subjects will be treated at 100 mg MK-3475 every 3 weeks for 6 cycles.

The Data Safety Review Team will make a determination if dose escalation to 200 mg is possible. The Data Safety Review Team automatically meets after 3 subjects have been enrolled and treated; however, a meeting may be called sooner, if deemed necessary.

